### Appendix 3      ECOG Performance Scale

ECOG Grade	Performance
0	Fully active, able to carry on all pre-disease performance without restriction.
1	Restricted in physically strenuous activity, but ambulatory and able to carry out work of a light or sedentary nature, e.g., light house work, office work.
2	Ambulatory and capable of all self-care, but unable to carry out any work activities. Up and about more than 50% of waking hours.
3	Capable of only limited self-care, confined to bed or chair more than 50% of waking hours
4	Completely disabled. Cannot carry on any self-care. Totally confined to bed or chair.
5	Dead

## Appendix 4      The International Workshop Criteria

The designation of complete response (CR) requires the following (Table 1):

1. Complete disappearance of all detectable clinical evidence of disease and disease-related symptoms if present before therapy.
- 2a. Typically (F)fluorodeoxyglucose (FDG)-avid lymphoma: in patients with no pretreatment positron emission tomography (PET) scan or when the PET scan was positive before therapy, a post-treatment residual mass of any size is permitted as long as it is PET negative.
- 2b. Variably FDG-avid lymphomas/FDG avidity unknown: in patients without a pretreatment PET scan, or if a pretreatment PET scan was negative, all lymph nodes and nodal masses must have regressed on computed tomography (CT) to normal size ( $\leq 1.5$  cm in their greatest transverse diameter for nodes  $> 1.5$  cm before therapy). Previously involved nodes that were 1.1 to 1.5 cm in their long axis and more than 1.0 cm in their short axis before treatment must have decreased to  $\leq 1.0$  cm in their short axis after treatment.
3. The spleen and/or liver, if considered enlarged before therapy on the basis of a physical examination or CT scan, should not be palpable on physical examination and should be considered normal size by imaging studies, and nodules related to lymphoma should disappear. However, determination of splenic involvement is not always reliable because a spleen considered normal in size may still contain lymphoma, whereas an enlarged spleen may reflect variations in anatomy, blood volume, the use of hematopoietic growth factors, or causes other than lymphoma.
4. If the bone marrow was involved by lymphoma before treatment, the infiltrate must have cleared on repeat bone marrow biopsy. The biopsy sample on which this determination is made must be adequate (with a goal of  $> 20$  mm unilateral core). If the sample is indeterminate by morphology, it should be negative by immunohistochemistry. A sample that is negative by immunohistochemistry but that demonstrates a small population of clonal lymphocytes by flow cytometry will be considered a CR until data become available demonstrating a clear difference in patient outcome.

**Table 1: Response Definitions for Clinical Trials**

Response	Definition	Nodal Masses	Spleen, Liver	Bone Marrow
CR	Disappearance of all evidence of disease	(a) FDG-avid or PET positive prior to therapy; mass of any size permitted if PET negative (b) Variably FDG-avid or PET negative; regression to normal size on CT	Not palpable, nodules disappeared	Infiltrate cleared on repeat biopsy; if indeterminate by morphology, immunohistochemistry should be negative
PR	Regression of measurable disease and no new sites	≥ 50% decrease in SPD of up to 6 largest dominant masses; no increase in size of other nodes (a) FDG-avid or PET positive prior to therapy; 1 or more PET positive at previously involved site (b) Variably FDG-avid or PET negative; regression on CT	≥ 50% decrease in SPD of nodules (for single nodule in greatest transverse diameter); no increase in size of liver or spleen	Irrelevant if positive prior to therapy; cell type should be specified
SD	Failure to attain CR/PR or PD	(a) FDG-avid or PET positive prior to therapy; PET positive at prior sites of disease and no new sites on CT or PET (b) Variably FDG-avid or PET negative; no change in size of previous lesions on CT		
Relapsed disease or PD	Any new lesion or increase by ≥ 50% of previously involved sites from nadir	Appearance of a new lesion(s) > 1.5 cm in any axis, ≥ 50% increase in SPD of more than 1 node, or ≥ 50% increase in longest diameter of a previously identified node > 1 cm in short axis Lesions PET positive if FDG-avid lymphoma or PET positive prior to therapy	> 50% increase from nadir in the SPD of any previous lesions	New or recurrent involvement

CR = complete remission

FDG = (F)fluorodeoxyglucose

PET = positron emission tomography

CT = computed tomography

PR = partial remission

SPD = sum of the product of the diameters

SD = stable disease

PD = progressive disease

Reprinted with permission. © 2008 American Society of Clinical Oncology. All rights reserved.

Cheson, BD et al: J Clin Oncol 25(5), 2007:579-86.

The use of the above definition for CR and that below for partial response (PR) eliminates the category of complete response unconfirmed (CRu).

The designation of PR requires all of the following (Table 1):

1. At least a 50% decrease in the sum of the product of the diameters (SPD) of up to 6 of the largest dominant nodes or nodal masses. These nodes or masses should be selected according to all of the following: they should be clearly measurable in at least 2 perpendicular dimensions; if possible they should be from disparate regions of the body; and they should include mediastinal and retroperitoneal areas of disease whenever these sites are involved.
2. No increase should be observed in the size of the other nodes, liver, or spleen.
3. Splenic and hepatic nodules must regress by  $\geq 50\%$  in their SPD or, for single nodules, in the greatest transverse diameter.
4. With the exception of splenic and hepatic nodules, involvement of other organs is usually assessable and no measurable disease should be present.
5. Bone marrow assessment is irrelevant for determination of a PR if the sample was positive before treatment. However, if positive, the cell type should be specified (eg, large-cell lymphoma or small neoplastic B cells). Patients who achieve a CR by the above criteria, but who have persistent morphologic bone marrow involvement will be considered partial responders.  
When the bone marrow was involved before therapy and a clinical CR was achieved, but with no bone marrow assessment after treatment, patients should be considered partial responders.
6. No new sites of disease should be observed.
7. Typically FDG-avid lymphoma: for patients with no pretreatment PET scan or if the PET scan was positive before therapy, the post-treatment PET should be positive in at least 1 previously involved site.
8. Variably FDG-avid lymphomas/FDG-avidity unknown: for patients without a pretreatment PET scan, or if a pretreatment PET scan was negative, CT criteria should be used.  
In patients with follicular lymphoma or mantle-cell lymphoma, a PET scan is only indicated with 1 or at most 2 residual masses that have regressed by more than 50% on CT; those with more than 2 residual lesions are unlikely to be PET negative and should be considered partial responders.

Stable disease (SD) is defined as the following (Table 1):

1. A patient is considered to have SD when he or she fails to attain the criteria needed for a CR or PR, but does not fulfill those for progressive disease (see Relapsed Disease [after CR]/Progressive Disease [after PR, SD]).
2. Typically FDG-avid lymphomas: the PET should be positive at prior sites of disease with no new areas of involvement on the post-treatment CT or PET.
3. Variably FDG-avid lymphomas/FDG-avidity unknown: for patients without a pretreatment PET scan or if the pretreatment PET was negative, there must be no change in the size of the previous lesions on the post-treatment CT scan.

Relapsed Disease (after CR)/Progressive Disease (after PR, SD) (Table 1)

Lymph nodes should be considered abnormal if the long axis is more than 1.5 cm regardless of the short axis. If a lymph node has a long axis of 1.1 to 1.5 cm, it should only be considered abnormal if its short axis is more than 1.0. Lymph nodes  $\leq 1.0 \times \leq 1.0$  cm will not be considered as abnormal for relapse or progressive disease.

1. Appearance of any new lesion more than 1.5 cm in any axis during or at the end of therapy, even if other lesions are decreasing in size. Increased FDG uptake in a previously unaffected site should only be considered relapsed or progressive disease after confirmation with other modalities. In patients with no prior history of pulmonary lymphoma, new lung nodules identified by CT are mostly benign. Thus, a therapeutic decision should not be made solely on the basis of the PET without histologic confirmation.
2. At least a 50% increase from nadir in the SPD of any previously involved nodes, or in a single involved node, or the size of other lesions (eg, splenic or hepatic nodules). To be considered progressive disease, a lymph node with a diameter of the short axis of less than 1.0 cm must increase by  $\geq 50\%$  and to a size of 1.5 x 1.5 cm or more than 1.5 cm in the long axis.
3. At least a 50% increase in the longest diameter of any single previously identified node more than 1 cm in its short axis.
4. Lesions should be PET positive if observed in a typical FDG-avid lymphoma or the lesion was PET positive before therapy unless the lesion is too small to be detected with current PET systems ( $< 1.5$  cm in its long axis by CT).  
Measurable extranodal disease should be assessed in a manner similar to that for nodal disease. For these recommendations, the spleen is considered nodal disease. Disease that is only assessable (eg, pleural effusions, bone lesions) will be recorded as present or absent only, unless, while an abnormality is still noted by imaging studies or physical examination, it is found to be histologically negative.

Reprinted with permission. © 2008 American Society of Clinical Oncology. All rights reserved.  
Cheson, BD et al: J Clin Oncol 25(5), 2007:579-86.

In clinical trials where PET is unavailable to the vast majority of participants, or where PET is not deemed necessary or appropriate for use (eg, a trial in patients with MALT lymphoma), response should be assessed as above, but only using CT scans. However, residual masses should not be assigned CRu status, but should be considered partial responses.

Reprinted with permission. © 2008 American Society of Clinical Oncology. All rights reserved.  
Cheson, BD et al: J Clin Oncol 25(5), 2007:579-86.

---

1 INTRODUCTION

The purpose of this statistical analysis plan is to provide details of the statistical analyses that have been outlined within version 2.1 of the protocol for pralatrexate study PDX-017 dated 31 Oct 2011. The scope of this plan includes the interim and final analyses. The analyses detailed within this plan will help to evaluate the efficacy and safety of pralatrexate as sequential therapy in patients with peripheral T-cell lymphoma (PTCL) who have achieved an objective response following initial treatment of first-line cyclophosphamide, doxorubicin, vincristine, and prednisone (CHOP)-based regimen.

2 OBJECTIVES

2.1 Primary Objective

Determine the efficacy of pralatrexate compared to observation when administered to patients with previously undiagnosed PTCL who have achieved an objective response after completing at least 6 cycles of CHOP-based treatment.

2.2 Secondary Objective

Determine the safety of pralatrexate when administered following a course of CHOP-based treatment to patients with previously undiagnosed PTCL.

3 STUDY DESIGN

This is an international, multi-center, randomized, Phase 3, open-label study of sequential pralatrexate versus observation in patients with previously undiagnosed PTCL who have achieved an objective response following initial treatment with CHOP-based chemotherapy.

Upon documentation of an objective response following at least 6 cycles of a designated CHOP-based chemotherapy, confirmation of histopathology by independent review, and confirmation that all eligibility criteria are met, patients will be randomized in a 2:1 ratio to either pralatrexate or observation, according to a permuted block design (block sizes of 3) stratified by response per investigator at completion of CHOP-based therapy (complete response [CR] vs partial response [PR]).

Patients randomized to the Pralatrexate Arm will receive pralatrexate as an intravenous (IV) push administration over a minimum of 30 seconds up to a maximum of 5 minutes via a patent free-flowing IV line containing normal saline (0.9% sodium chloride [NaCl]) weekly for 3 weeks (\pm 1 day at each time point) of a 4-week cycle. The initial dose of pralatrexate will be 30 mg/m² which, based on protocol-defined criteria, may be reduced to 20 mg/m² with potential further reduction to 15 mg/m² and 10 mg/m². There will be sparse sampling for pharmacokinetics (PK). Pralatrexate will continue to be administered until a criterion for study treatment discontinuation is met or up to a maximum of 2 years.

Patients randomized to the Observation Arm will remain under observation, attend clinic visits every 4 weeks, and receive a follow-up phone call from a healthcare professional during each week 2 of 4 until a criterion for study treatment discontinuation is met for a maximum of 2 years.

All patients will receive vitamin supplementation, consisting of vitamin B₁₂ 1 mg intramuscularly (IM) every (q) 8-10 weeks and folic acid 1-1.25 mg by mouth (po) once a day (qd). Vitamin supplementation will begin at least 7 days prior to the projected initiation of pralatrexate/observation and continue throughout the study until the Initial Follow-up Visit.

Patients will be followed for safety until 35 (\pm 5) days after the study treatment discontinuation criteria are met. Patients will be followed to determine time to progressive disease (PD) and survival for up to 7 years from randomization or until 35 (\pm 5) days after the last dose of pralatrexate, whichever is longer. Patients who withdraw from treatment prior to PD without withdrawing consent will be followed for disease status whenever possible, even if subsequent therapy, including transplant, has been initiated prior to documented PD per central review, at least until the first interim analysis.

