### Treatment Plan:

This is an international, multi-center, randomized, Phase 3, open-label study of sequential pralatrexate versus observation in patients with previously undiagnosed PTCL who have achieved an objective response following initial treatment with CHOP-based chemotherapy. Upon documentation of completion of an objective response following at least 6 cycles of a designated CHOP-based chemotherapy confirmation of histopathology by independent review, and confirmation that all eligibility criteria are met, patients will be randomized in a 2:1 ratio to either pralatrexate or observation, according to a permuted block design with stratification factor of:

- Response per investigator at completion of CHOP-based therapy (complete response [CR] vs partial response [PR])

Patients randomized to the Pralatrexate Arm will receive pralatrexate as an intravenous (IV) push administered over a minimum of 30 seconds up to a maximum of 5 minutes via a patent free-flowing IV line containing normal saline (0.9% sodium chloride [NaCl]) weekly for

3 weeks ( $\pm$  1 day at each time point) of a 4-week cycle. The initial dose of pralatrexate will be 30 mg/m^2, which based on protocol-defined criteria, may be reduced to 20 mg/m^2 with potential further reductions to 15 and 10 mg/m^2. Pralatrexate will continue to be administered until a criterion for study treatment discontinuation is met or up to a maximum of 2 years.

Patients randomized to the Observation Arm will remain under observation, attend clinic visits every 4 weeks, and be contacted by a healthcare professional during week 2 of every 4-week period until a criterion for study treatment discontinuation is met.

All patients will receive vitamin supplementation, consisting of vitamin B12 1 mg intramuscular (IM) every 8-10 weeks and folic acid 1-1.25 mg by mouth (po) once a day (qd). Vitamin supplementation will begin at least 7 days prior to the projected initiation of pralatrexate/observation and continue throughout the study until the Initial Follow-up Visit.

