## 10.2 Patient Randomization

Each patient who signs an IC document for participation in this study will be assigned a unique screening number. The screening number consists of 7 digits; the first 4 digits will be the site number used for all study activities, and the final 3 digits will be a consecutive number starting with [REDACTED] (eg, the screening number for the fourth patient screened at site number [REDACTED] would be [REDACTED]).

Once it has been determined that a patient meets eligibility criteria as outlined in [Section 8.2](#), the site must randomize via interactive response technology (IRT), formally referred to as interactive voice response system (IVRS). The randomization treatment group and patient randomization number will be assigned at this time. Randomization of patients to either pralatrexate or observation must occur within 6 weeks following day 1 of the last planned cycle of CHOP-based chemotherapy. Please refer to the study binder for detailed instructions regarding randomization.

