## 15.5 Stratification

Patients meeting randomization eligibility criteria will be randomized 2:1 to the Pralatrexate Arm or the Observation Arm according to a permuted block design, balancing within the following stratum.

- Response per investigator at completion of CHOP-based therapy (CR vs PR)

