3.1 Stratification Factors

The randomization will be stratified by response per investigator at completion of CHOP-based therapy (CR vs PR).

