The sample size is based on comparing the treatment groups with respect to the primary efficacy endpoints of PFS and OS. Assuming proportional hazards, a true hazard ratio (HR) on OS of 0.73, and a 2:1 randomization (treatment:observation) with a total of 549 patients (366 in the treatment group vs 183 in the observation group), a total of 385 OS events (deaths) will provide at least 80% power to show $HR < 1.00$ using a 2-sided stratified log-rank test at a 0.05 significance level ($\alpha = 0.05$), assuming an accrual period of 54 months and a follow-up period of 30 months. For a HR on PFS of 0.67, a total of 280 PFS events (PD + deaths) will provide at least 80% power to show $HR < 1.00$ using a 2-sided stratified log-rank test at a 0.05 significance level.

Further assuming that PFS is exponentially distributed, that the median PFS in the control group is 10 months, and that uniform enrollment will occur over 54 months, under the alternative hypothesis that $HR = 0.67$, the 280th event will occur approximately 48 months after the first patient is randomized. Allos will set a data cut-off date for the primary efficacy analysis in anticipation of the 280th PFS event and 128th OS event.

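### The SAP fixes and discloses a block size of 3, the smallest possible at 2:1, in an open-label trial; anyone with a stratum's full cross-site list would know 44% of assignments in advance, though a single site would know far fewer (minor)

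*SAP*

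**What the plan says.** The synopsis of the protocol states: "This is an international, multi-center, randomized, Phase 3, open-label study of sequential pralatrexate versus observation". SAP section 3 says that "patients will be randomized in a 2:1 ratio to either pralatrexate or observation", by a "permuted block design (block sizes of 3) stratified by response per investigator at completion of CHOP-based therapy". There is one stratification factor: "The randomization will be stratified by response per investigator at completion of CHOP-based therapy (CR vs PR"). Site and region are not strata, so two lists, one for CR and one for PR, serve every site.

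The protocol does not give the block size. Section 15.5 says only that allocation is "according to a permuted block design, balancing within the following stratum". Neither document names a second block size or a random choice among sizes.

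Under Protocol section 10.2 the arm is released through the IRT once eligibility has been determined. Neither document says who may see cumulative assignments by stratum, or whether sites receive the SAP.

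**The concern.** At 2:1 a block of 3 holds two pralatrexate places and one observation place. The third place is therefore always determined by the first two, and an observation assignment in first place settles the rest of the block. Because treatment is open-label, each assignment is known once it is made. The only barriers to reading the next one are ignorance of the block size, which the SAP prints, and not seeing the other sites' assignments.

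Some staff plausibly have a cross-site view. Monitors visit every site (Protocol section 1) with direct access to source records (section 16.5.1). The sponsor or its designee must also count pralatrexate-arm patients across sites in order to stop PK sampling at 245 (section 10.4.1).

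If foreknowledge reached whoever decides on enrollment, that person could delay or withhold a frailer patient, or settle a borderline CR/PR call so that the patient enters the list with the preferred next assignment. Blinded central review of progression (Protocol section 15.7.1) protects how PFS events are judged. It does not protect who enters each arm, and it has no bearing on OS.

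**Working it through.** The documents give no predictability figure, so there is none to reproduce.

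**Inputs.** Block size 3, ratio 2:1 and the two strata come from SAP sections 3 and 3.1. The total is "549 patients (366 in the treatment group vs 183 in the observation group") in SAP section 3.2, which is 549/3 = 183 blocks. P is pralatrexate and O is observation.

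**1. Certain assignments, full list seen.** The three block orders are equally likely.

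| Order | Certain places | Certain P | Certain O |
|---|---|---|---|
| PPO | 3rd | 0 | 1 |
| POP | 3rd | 1 | 0 |
| OPP | 2nd and 3rd | 2 | 0 |

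- Certain per block: (1 + 1 + 2)/3 = 4/3. As a share: (4/3)/3 = 4/9 = 44.4%, or 549 × 4/9 = 244 patients if all blocks are complete.
- Certain P: (0 + 1 + 2)/3 = 1 per block, 1/3 = 33.3% of assignments.
- Certain O: 1/3 per block, 1/9 = 11.1% of assignments.

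**2. Best guess, full list seen.**

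- 1st place: 2/3.
- 2nd place: (2/3)(1/2) + (1/3)(1) = 2/3.
- 3rd place: 1.
- Mean: (2/3 + 2/3 + 1)/3 = 7/9 = 77.8%.
- Always naming pralatrexate scores 2/3 = 66.7%, so the gain is 11.1 points.

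**3. What one site can know.** Assume K equally recruiting sites share each list, and that a site sees only its own patients but knows which block places they hold. The second assumption is generous to the site.

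- 2nd place is certain when the order is OPP and the site holds the 1st place: 1/(3K).
- 3rd place is certain when the site holds the O place (orders POP and OPP) or both P places (order PPO): (1/3)(2/K + 1/K²).
- Share certain: [1/(3K) + 2/(3K) + 1/(3K²)]/3 = 1/(3K) + 1/(9K²).

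| K (assumed) | Share certain |
|---|---|
| 1 | 4/9 = 44.4% |
| 5 | 0.0667 + 0.0044 = 7.1% |
| 20 | 0.0167 + 0.0003 = 1.7% |
| 50 | 0.0067 + 0.00004 = 0.7% |

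**4. Other block schemes, full list seen.** The fixed sizes are exact. The mixture was simulated with equal probability per size and an observer who knows the set of sizes but not the draw.

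| Scheme | Certain | Best guess |
|---|---|---|
| Fixed 3 | 44.4% | 77.8% |
| Fixed 6 | 13/45 = 28.9% | 74.4% |
| Fixed 9 | 21.4% | 72.8% |
| Random 3, 6, 9 | about 4% | about 74% |

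Random sizes mainly remove certainty. Best-guess accuracy falls by only about 4 points, because 2:1 allocation already makes pralatrexate the better guess.

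**5. Price in balance.** The worst point inside a block of 9 is three O in a row (3 against an expected 1) or six P in a row (6 against an expected 4). Either is 2 patients from exact 2:1. In a block of 3 the corresponding figure is 2/3 of a patient.

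**The case against.** The strongest reply is that the 44% describes someone who does not enroll patients. Selection bias needs foreknowledge in the person deciding on entry, and nothing in the documents says that cumulative assignments reach sites. A reader might infer that 44% of assignments are predictable at an enrolling site. That is not supported: site is not a stratum, the lists interleave patients from all sites, and step 3 gives the much smaller site-level shares. This part of the objection stands and limits the point.

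Other strong readings also fail:

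- **That having only two strata raises the figure.** The 4/9 holds in any stratum with complete blocks. Two lists are easier to follow, but sharing them across sites is itself a protection; blocks of 3 within site would be worse.
- **That foreknowledge could load one arm with PR patients.** CR and PR are blocked separately, and the primary tests are stratified by the IRT strata (SAP sections 8.5.1 and 8.5.2). Recorded PR status cannot drift between arms beyond an incomplete block.
- **That the investigator controls eligibility and timing freely.** Histology needs independent confirmation before randomization (Protocol section 12.2.2). Laboratory limits apply and imaging must be within 21 days (section 8.3). Randomization must fall within 6 weeks of day 1 of the last planned CHOP cycle (section 10.1). Some discretion remains over the date and the CR/PR call.
- **That analysis can do nothing.** SAP sections 4.4 and 8.5.4 plan models with IPI, histology and region. These address measured factors only.

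It is also fair to say that three quarters of the certain assignments (33.3 of 44.4 points) are pralatrexate, which a guesser would name anyway, and that the protocol already leaves the block size out.

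**Conclusion.** The point holds as a minor, avoidable weakness. The plan uses the most predictable permuted-block scheme available at 2:1 and prints the block size in the SAP. The 44.4% and 77.8% apply only to an observer who both knows the size and sees a stratum's full cross-site list. Sponsor or monitoring staff are plausible examples, but the documents neither grant nor restrict that view. The site-level figures rest on assumed numbers of equally recruiting sites.

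The documents show no actual subversion and contain no contradiction on this matter. What remains is a conditional risk of selection on timing, frailty or a borderline response call, which central review does not address and covariate adjustment addresses only in part.

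**What to change.** For patients not yet randomized, have the IRT draw block sizes at random from 3, 6 and 9 within each of the CR and PR strata. Replace the block size in SAP section 3 with a statement that the sizes are held in a restricted randomization specification. Keep that specification, and cumulative assignments by stratum, with the randomization statistician and the IRT vendor only, and state this restriction in the plan.

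The cost is an IRT list change, a text edit, and a transient departure from 2:1 of a few patients per stratum, negligible in 549. The change does nothing for patients already randomized, and the documents do not say how many that is. Staff who need arm-level data for safety or PK tracking can still have it; what should be withheld is the running order of assignments within a stratum.
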